7.1.1.3 FFU Visit Clinical Response Assessment

At the follow-up assessment (FFU), subjects will be re-evaluated by the Investigator for clinical response and will be reported for the micro-ITT and CE-FFU population by treatment group.

The investigator will determine whether or not the subject meets the criteria of 1 of the following clinical outcomes:

- **Clinical Success:** Sufficient resolution of signs and symptoms at the Final Follow-up visit such that no additional systemic antimicrobial therapy is required for the current infection.
- **Clinical Failure:** No apparent response to therapy or persistence of signs and symptoms of infection or reappearance of signs and symptoms at or before the Final Follow-up visit such that use of additional systemic antimicrobial therapy for the current infection is required.

- **Indeterminate:** Final Follow-up visit not completed.

Overall (Sustained) Response (based on the investigator's assessment) at FFU is determined as defined in [Table 6](#).

Table 6 Overall Investigator's Assessment of Clinical Response at FFU Visit

Overall Clinical Response at PTE Visit	Clinical Response at FFU Visit	Overall Clinical Response at FFU Visit
Success	Success	(Sustained) Clinical Cure
Success	Failure	Clinical Failure
Success	Indeterminate	Indeterminate
Failure	Success	Clinical Failure
Failure	Failure	Clinical Failure
Failure	Indeterminate	Clinical Failure
Indeterminate	Success	Indeterminate
Indeterminate	Failure	Clinical Failure
Indeterminate	Indeterminate	Indeterminate

PTE = post-therapy evaluation; FFU = Final Follow-up

7.1.2 Microbiologic response

Per-pathogen and per-subject microbiologic response will be programmatically determined at the EOT and PTE Visits in the micro-ITT and ME populations (by definition subjects in the ME population cannot have an indeterminate response).

Microbiological response will be derived using electronically transferred microbiology data from the central laboratory (or local laboratory if central data are not available).

Overall per-pathogen microbiological response at PTE is determined as follows (Table 7) from the per-pathogen microbiological responses at the EOT and PTE Visits.

7.1.2.1 Pathogen Determination

A pathogen is defined as bacteria implicated as causative in a subject's cystitis. Baseline pathogens and post-baseline pathogens will be identified for each patient programmatically with a manual review and confirmation. Sponsor determination review will be performed in a blinded manner by Sponsor's internal microbiology review committee. Details are documented in the [Pathogen and CE Review Plan: PTK0796-uUTI-17201²](#).

7.1.2.2 Microbiologic Response

Per-pathogen microbiological response will be programmatically determined at the EOT and PTE Visits in the micro-ITT and ME populations (by definition subjects in the ME population cannot have an indeterminate response).

Pathogen microbiological outcome categories are: eradication, persistence, and indeterminate and these are defined in [Table 7](#). Favorable microbiological outcomes include eradication. Unfavorable microbiological outcomes include persistence or indeterminate.

Table 7 Pathogen Microbiological Outcome Categories at EOT and PTE

Category	Criteria	Interpretation
Eradication	Urine specimen shows absence of the original baseline pathogen or the baseline pathogen grew at $<10^4$ CFU/mL at visit.	Favorable
Persistence	Urine culture shows continued presence (defined as $\geq 10^4$ CFU/mL) of the original baseline pathogen(s) at visit.	Unfavorable
Indeterminate	Urine specimen was not available to culture (or the culture result was not interpretable).	Unfavorable

*for PTE visit use Overall Clinical Response at PTE

Per-subject microbiological responses will be based on per-pathogen outcomes. To have an overall per subject favorable microbiologic response, the outcome for each baseline pathogen must be favorable. If the outcome for any baseline pathogen is unfavorable, the subject will be considered to have an unfavorable per-subject microbiologic response. Subjects with an indeterminate response for all baseline pathogens will be considered to have an indeterminate per-subject microbiologic response. Subjects with at least one indeterminate response for a baseline pathogen when all other baseline pathogens have a favorable response will be considered to have an indeterminate per-subject microbiologic response.

Table 8 Per-Subject Microbiologic Response

Condition	Microbiologic Response at Visit	Per-Subject Microbiologic Response at Visit
All per-pathogen microbiological responses at visit	Favorable (Eradication)	Favorable
Any per-pathogen microbiological response at visit	Unfavorable (Persistence)	Unfavorable
All per-pathogen microbiological responses at visit	Indeterminate	Indeterminate
At least one per-pathogen microbiological response at visit when other responses are Favorable (Eradication)	Indeterminate	Indeterminate

[figure not shown]
Per-pathogen and per-subject overall microbiological responses at PTE are determined as follows (Table 9) from the per-pathogen and per-subject microbiological responses at the EOT and PTE Visits:

Table 9 Microbiologic Response at PTE

Microbiologic Response at EOT Visit	Microbiologic Response at PTE Visit	Overall Microbiologic Response at PTE
Favorable	Favorable	Favorable
Favorable	Unfavorable	Unfavorable
Favorable	Indeterminate	Indeterminate
Unfavorable	Favorable	Unfavorable
Unfavorable	Unfavorable	Unfavorable
Unfavorable	Indeterminate	Unfavorable
Indeterminate	Favorable	Indeterminate
Indeterminate	Unfavorable	Unfavorable
Indeterminate	Indeterminate	Indeterminate

Favorable is defined as the eradication of the baseline pathogen.
 Unfavorable is defined as the persistence of a baseline pathogen
 EOT = end of treatment; PTE = post-therapy evaluation.

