7.3.2 Per-Subject Microbiological Response

The per-subject microbiological (overall) response at the EOT and PTE Visits in the micro-ITT, ME-EOT and ME-PTE populations will be determined to support the clinical findings.

The number and percentage of subjects classified with a favorable (eradication) and unfavorable (persistence and indeterminate) microbiological response (by definition, indeterminates are excluded from the ME population) will be tabulated for both treatment groups. Exact 95% confidence intervals will be determined for the point estimates of the favorable microbiologic outcome rates in each treatment group and for difference from nitrofurantoin (omadacycline - nitrofurantoin).

Concordance of microbiological outcome with clinical outcome at EOT and PTE visits for the micro-ITT and ME populations will be provided.

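### The footnote to SAP Table 7 puts the clinical response into the PTE microbiologic outcome, contradicting the table's culture criteria and Table 9

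*SAP*

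**What the plan says.** SAP Section 7.1 lists the Overall Microbiologic response at PTE as a secondary endpoint in the micro-ITT and ME-PTE populations. Four pieces of SAP text govern how it is derived.

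- **Data source (Section 7.1.2).** "Microbiological response will be derived using electronically transferred microbiology data from the central laboratory", with the local laboratory as back-up.
- **Visit-level categories (Section 7.1.2.2).** The title is "Table 7 Pathogen Microbiological Outcome Categories at EOT and PTE". Eradication means the baseline pathogen is absent or below 10^4 CFU/mL. Persistence begins "Urine culture shows continued presence" and is set at 10^4 CFU/mL or more. Indeterminate means there is no specimen or the culture cannot be interpreted. No row has a clinical criterion. The footnote then says "for PTE visit use Overall Clinical Response at PTE".
- **Overall PTE response, first statement (Section 7.1.2).** "Overall per-pathogen microbiological response at PTE is determined as follows (Table 7"; the sentence goes on to name the per-pathogen microbiological responses at EOT and PTE as the inputs.
- **Overall PTE response, second statement (end of Section 7.1.2.2).** "Per-pathogen and per-subject overall microbiological responses at PTE are determined as follows (Table 9", from the same inputs. Table 9 crosses the EOT result with the PTE result and defines Favorable as eradication.

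The term in the footnote is defined elsewhere: Table 5 in Section 7.1.1.2 derives it from the investigator's EOT and PTE assessments. Section 7.3.2 also plans a comparison of the two outcomes: "Concordance of microbiological outcome with clinical outcome at EOT and PTE visits for the micro-ITT and ME populations will be provided".

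**The concern.** The footnote is an instruction for an endpoint that the SAP says is determined programmatically, and it names the wrong kind of variable. If it is followed, the PTE culture drops out of the visit-level PTE outcome and the investigator's rating takes its place.

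The pointer in Section 7.1.2 makes this worse. It sends the reader to Table 7 for the overall PTE response, and the only text there specific to PTE is the footnote.

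The microbiologic response is planned as support for the clinical findings, and response by causative pathogen is a secondary objective. An outcome partly filled in from the clinical rating gives less independent support. A rating per subject also cannot give separate results for two baseline pathogens. The concordance table at PTE would compare the clinical response with something partly built from it.

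**Working it through.** The SAP gives no figure to reproduce here. The check compares the passages and then counts the outcomes that change.

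**1. Passages side by side.** Every other relevant passage uses the culture:
- SAP Section 4.5 generally requires interpretable EOT and PTE cultures for the ME populations, and treats the baseline species at 10^4 CFU/mL or more at any later visit as persisting.
- Protocol Section 8.6.2.2 has the same persistence rule, and SAP Section 9 declares no change from the protocol.
- Section 7.1.2 takes the response from laboratory data.
- Table 9 has no clinical input.

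Only the footnote uses the clinical response.

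**2. Assumption needed to apply the footnote.** Success = Favorable, Failure = Unfavorable, Indeterminate = Indeterminate. The SAP gives no such mapping.

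**3. Two rules compared.**
- Culture rule: Table 9 (EOT culture, PTE culture).
- Literal footnote: Table 9 (EOT culture, Overall Clinical Response at PTE).

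Each of the three inputs has three levels, so there are 3 × 3 × 3 = 27 combinations.

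- **EOT Favorable (9 cells).** Table 9 returns whatever stands in its PTE column, so the result changes whenever PTE culture and clinical response differ: 9 − 3 = 6 cells.
- **EOT Unfavorable (9 cells).** Table 9 always returns Unfavorable: 0 cells.
- **EOT Indeterminate (9 cells).** Table 9 returns Unfavorable if the PTE entry is Unfavorable, otherwise Indeterminate. The result changes when exactly one of PTE culture and clinical response is unfavorable: 2 + 2 = 4 cells.

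Total 6 + 0 + 4 = 10 of 27:

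| EOT culture | PTE culture | Clinical response | Culture rule | Literal footnote |
|---|---|---|---|---|
| Favorable | Favorable | Failure | Favorable | Unfavorable |
| Favorable | Favorable | Indeterminate | Favorable | Indeterminate |
| Favorable | Unfavorable | Success | Unfavorable | Favorable |
| Favorable | Unfavorable | Indeterminate | Unfavorable | Indeterminate |
| Favorable | Indeterminate | Success | Indeterminate | Favorable |
| Favorable | Indeterminate | Failure | Indeterminate | Unfavorable |
| Indeterminate | Favorable | Failure | Indeterminate | Unfavorable |
| Indeterminate | Unfavorable | Success | Unfavorable | Indeterminate |
| Indeterminate | Unfavorable | Indeterminate | Unfavorable | Indeterminate |
| Indeterminate | Indeterminate | Failure | Indeterminate | Unfavorable |

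**4. Effect on the favorable rate.** Section 7.3.2 groups persistence and indeterminate together as unfavorable. On that two-way split, 4 of the 10 cells matter, all with EOT Favorable: rows 1 and 2 lose a favorable result, rows 3 and 5 gain one. The change in the favorable rate is therefore

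P(EOT favorable, PTE not favorable, clinical success) − P(EOT favorable, PTE favorable, clinical not success).

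It can have either sign. The documents give none of these joint probabilities.

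**5. How far the result follows the clinical response.** Of the 9 combinations of EOT culture and clinical response, the literal rule returns the clinical category in 6. It does not in 3: Unfavorable with Success gives Unfavorable, Unfavorable with Indeterminate gives Unfavorable, and Indeterminate with Success gives Indeterminate.

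**The case against.** The strongest reply is that this is a slip with an obvious cure. The likely intended term is the Overall Microbiologic Response. SAP Section 5.1.2 says that imputations like those for the overall clinical response were applied to the microbiological endpoints, which fits that reading. The two sentences introducing the overall PTE response name the same inputs, so they state one rule with a misnumbered table reference, not two rival derivations. With no mapping from Success and Failure to eradication and persistence, a programmer would probably raise a query. The asterisk has no visible anchor in the table, though it may have been lost when the PDF was read.

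Much of this stands: the culture rule is clearly the better-supported reading. But the SAP nowhere says that the footnote is an error, and a query is not assured. The contradiction has to be removed from the text.

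A reader might also infer that the PTE microbiologic endpoint would simply copy the clinical endpoint, with complete concordance and all symptom-free persistence hidden. The documents do not support that. The endpoint passes through Table 9, where an Unfavorable EOT culture stays Unfavorable whatever the clinical rating, and Section 4.5 carries EOT microbiological failures into ME-PTE. A subject with EOT persistence and clinical success remains discordant. Only persistence or regrowth without an Unfavorable EOT culture can be masked.

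**Conclusion.** The contradiction is real and concerns an operative derivation rule. Read literally, and under the mapping assumed above, the footnote replaces the visit-level PTE culture outcome with the clinical response and makes the overall PTE response a hybrid of EOT culture and clinical response. For subjects with a Favorable EOT culture, the overall result would equal the clinical response: regrowth at PTE without symptoms would count as Favorable, and a negative PTE culture with clinical failure as Unfavorable. Subjects Unfavorable at EOT are not affected.

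The size is 10 of 27 combinations, counted as unweighted cells and not as subjects. It is tempting to size the effect by setting the clinical success rate of 0.82 from SAP Section 3.1 against an assumed eradication rate. That would mislead. The 0.82 is a planning assumption for the primary clinical endpoint, which is analyzed in the ITT population; the documents give no eradication rates for this trial; and such a sum leaves out Table 9.

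The effect is confined to a secondary endpoint and to the PTE concordance table, which is weakened but not made circular. The primary endpoint and the adaptive rules use the clinical response at PTE by design and are not affected. That the footnote is a misreference is an inference.

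**What to change.** Make two wording changes by SAP amendment before database lock.

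1. Delete the Table 7 footnote, or replace it with: *for the PTE visit, apply the culture criteria above, then derive the Overall Microbiologic Response at PTE from Table 9*.
2. In Section 7.1.2, change the reference for the overall per-pathogen response at PTE from Table 7 to Table 9.

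If the sponsor does intend clinical failure to count toward the PTE microbiologic outcome in some situation, that should be an explicit row with its own criterion, not a substitution of one endpoint for another.

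The cost is two edits and a check that any derivation already programmed follows Table 9. No new data or analyses are needed.

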7.1.2.3 Other microbiological endpoints

7.1.3 UTI Signs and Symptoms Assessment

Subject assessment of UTI signs and symptoms severity will be collected at Screening, and daily through EOT (including self-completion by subject at home on Days 2, 4 and 6), at PTE and at FFU via the UTISA questionnaire.

The UTISA is a subject completed, 14-item questionnaire that assesses the levels of ‘severity’ and ‘bothersomeness’ for each of the seven most frequently reported symptoms and signs of UTI:

- Frequency
- Urgency
- Pain/burning on urination
- Incomplete voiding
- Pain in pelvic area
- Low back pain

- Blood in urine

[figure not shown]
Each item has a Likert-type response scale, the ‘severity’ item response options being ‘did not have’, ‘mild’, ‘moderate’, ‘severe’, scored 0–3; and the bothersomeness item response options being ‘not at all’, ‘a little’, ‘moderately’, ‘a lot’, scored 0–3.

Total scores of the 7 items for the severity of signs and symptoms scores and total scores for the 7 items related to the bothersomeness will be calculated for each subject and visit. The total scores for severity and bothersomeness will be between 0 and 21. The total score 0 is indicating the least severity of signs and symptoms and a total score of 21 is indicating the worst severity. For bothersomeness, the total score 0 is indicating the least bothersome score and a total score of 21 is indicating the most bothersome score.

The bothersomeness questions are only answered if the subject reported presence of the sign/symptom, otherwise this answer is omitted by design.

For calculating the individual total subject score by timepoint for both sub-scales, the scores of non-missing item scores are summed up and divided by the number of non-missing items and then multiplied by 7. If less than 4 items are answered for each sub-scale, the total score is set to ‘missing’ for the sub-scale of the subject.

Frequency of subjects with resolution of all symptoms, without occurrence of new symptoms (in comparison to baseline), and no worsening of baseline symptoms will be provided by timepoint.

7.2 Primary Efficacy Endpoint Analysis

The primary efficacy endpoint is investigator's assessment of clinical response at PTE in the ITT population, as measured by the number of subjects in each treatment group.

The primary efficacy outcome is the percentage of subjects with an overall clinical success at the PTE Assessment in the ITT population. Each omadacycline treatment group will be compared to nitrofurantoin group for non-inferiority (pairwise). This non-inferiority test will be based on the lower limit of the 2-sided exact 95% confidence interval (CI).

The null and alternative hypotheses are as follows for overall clinical success:

$$H_0 : p_1 - p_2 \leq -\Delta \text{ and } H_1 : p_1 - p_2 > -\Delta,$$

where p_1 is the primary efficacy success rate in each of the omadacycline treatment group, p_2 is the primary efficacy success rate of nitrofurantoin group, and Δ is the non-inferiority margin of 10%. No multiplicity adjustment will be used to account for multiple doses being compared to levofloxacin.

To test the null hypothesis, a 2-sided 95% CI for the observed difference in primary outcome rates (omadacycline group minus nitrofurantoin group) will be calculated. If the lower limit of the 95% CI for the difference exceeds -10% , then the null hypothesis will be rejected and the non-inferiority of omadacycline to nitrofurantoin will be declared for that dose.

The number and percentage of subjects in each treatment group defined as an overall clinical success, failure and indeterminate (subjects with missing data or who are lost to follow-up) will be tabulated, as will the overall category combining failure and indeterminate.

In addition, 95% credible intervals will be provided for the difference in success rates using the modeling as follows. Assuming the likelihood for number of responders to have binomial distribution [$Y_i \sim \text{Bin}(n_i, p_i)$] and non-informative beta priors [$p_i \sim \text{Beta}(0.5, 0.5)$]. The posterior probability of non-inferiority will be computed as $P(p_{\text{OMC}} - p_{\text{N}} > -0.1 \mid \text{data})$ for assessment.

Additional sensitivity analyses are described in [Section 7.5.2](#).

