3.1 Sample Size Considerations

Enrollment of a total of approximately 225 subjects is planned. The Bayesian posterior probability that the clinical success rate at the PTE Visit is within 0.10 of that of the nitrofurantoin group will be estimated for each omadacycline dose group. The target probability is 0.80. If the true underlying clinical success rates for the nitrofurantoin and omadacycline dose groups are 0.82, then the sample size of $N = 50$ per treatment has approximately 79% power/probability to yield the target probability ($N = 53$ per treatment for 80% power).

The sample size may be increased for a particular omadacycline dose group by changing the randomization ratio and/or dropping a dose group to achieve improved power/probability of achieving the target probability that clinical success rates for a dose group is within 0.10 of that of the nitrofurantoin group. If required to improve the precision of the interim or projected final

analyses estimates of response rates or posterior probabilities, sample size may be increased to a maximum sample size of 300 patients.

The decisions affecting changes of randomization to treatment groups, hence affecting total sample size, will be based on the recommendation of the DMC at interim analyses in an unblinded manner. Statistical details relevant to pre-defined decision rules for the DMC are documented in the DMC SAP⁽¹⁾.

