4 ANALYSIS POPULATIONS

4.1 Intent-to-Treat Population

The intent-to-treat (ITT) population will consist of all randomized subjects regardless of whether or not the subject received test article.

A subject is considered randomized when the IxRS provides the test article assignment by providing the kit number (ie, completes a randomization transaction). Subjects in this population will be summarized according to randomized test article assignment.

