8.2 Duration of Exposure to Test Article and Compliance

Exposure summary by treatment group will be presented for the safety, micro-ITT, and CE-PTE populations.

Duration of exposure to test article (days) for the individual subject is the number of days subject received test article (last day of study test article – first day of test article + 1). Duration of treatment (days) will be summarized using descriptive statistics. The distribution of subjects by the total number of days on test article (1-3, 4-5, 6-7, and > 7 days) will be presented.

The degree of test article compliance will be determined by presenting the number of tablets taken as a percentage of the number required by the protocol.

$$\%Compliance = 100\% * \frac{\text{Actual number of tablets taken}}{\text{Expected \#of tablets}}$$

The last dose date is the last day the subject is expected to receive test article based on the length of therapy determined by the investigator or the actual last date the subject took test article, if s/he prematurely discontinued test article. For subjects who complete the study, the last dose day used in the denominator calculation will be the last expected dosing day. For early termination subjects, the last day of study drug used in the denominator calculation will be the last expected dosing day before termination day. A subject is expected to receive a total of 38 tablets during the treatment phase for subjects enrolled at the time preceding protocol amendment 2, and 56 tablets with amendment 2. For detail on dosing schedules refer to Table 2 of the study protocol.

Descriptive statistics for treatment and fasting compliance will be presented by treatment group and by protocol version at which a subject entered the study.

Number of subjects and percentage with a compliance $\geq 80\%$ will be presented. A summary of compliance with the pre- and post-dose fasting requirements will also be provided. The percent fasting compliance will be determined based on the total doses taken where fasting is required. The percentage of subjects who were < 50%, 50% to < 80%, and 80% to 100% compliance with the pre-dose and post-dose fasting requirements met will be summarized.

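### Group 4 opened after at least 145 subjects, but the visible primary analysis compares it with every nitrofurantoin subject and shows no concurrent-control or period-adjusted result

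*SAP*

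**What the plan says.** Protocol 7.4 records the decision to add the twice-daily omadacycline arm and supports it with a blinded tolerability review of the first 145 subjects. Protocol 5.1 still describes assignment to one of three omadacycline regimens or nitrofurantoin, which fits four arms before the change. SAP 3.2 has five arms at 1:1:1:1:1. SAP 3.1 plans about 225 subjects and allows that "sample size may be increased to a maximum sample size of 300 patients".

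SAP 7.2 sets the comparison: "Each omadacycline treatment group will be compared to nitrofurantoin group for non-inferiority (pairwise"). The decision rule is: "This non-inferiority test will be based on the lower limit of the 2-sided exact 95% confidence interval (CI"). If the lower limit is above -10%, "the non-inferiority of omadacycline to nitrofurantoin will be declared for that dose". The same section adds a posterior probability of non-inferiority from independent binomials with Beta(0.5, 0.5) priors, one rate per arm. The population is ITT, defined in SAP 4.1: "The intent-to-treat (ITT) population will consist of all randomized subjects regardless of whether or not the subject received test article".

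The visible part of 7.2 has no restriction to concurrent controls, no stratum and no period term. The only visible use of protocol version as a summary factor is for compliance, reported "by treatment group and by protocol version at which a subject entered the study" (SAP 8.2).

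**The concern.** Nitrofurantoin subjects randomised before Group 4 opened had no chance of receiving it. Randomisation does not protect that part of the comparison. If nitrofurantoin success was lower in the early period, the pooled control rate is too low and Group 4 looks better than it is. If it was higher, Group 4 looks worse. The same pooled rate feeds the confidence interval and the posterior, so both move together.

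At stake is the estimate for the added arm, in a trial meant to help choose regimens for later studies (Protocol 3.2). A poor regimen could look acceptable, or a good one could be dropped.

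**Working it through.** **The plan's own figure.** The plan gives none for this comparison. The nearest is the sample-size statement in SAP 3.1 (true rates 0.82, target 0.80, about 79% at 50 per arm and 80% at 53). Enumerating the 7.2 model gives 69.2% and 69.5%; a target of 0.70 would give 79.8% and 81.2%. That mismatch is a separate matter and does not affect what follows.

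**Inputs from the documents.** At least 145 subjects before Group 4 (Protocol 7.4); N = 225 or 300 and a rate of 0.82 (SAP 3.1); five equal arms after (SAP 3.2); margin 0.10 and Beta(0.5, 0.5) priors (SAP 7.2).

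**Assumptions.** Equal allocation over four arms before the switch, a switch at exactly 145, no later change of ratio, and drifts of 5 and 10 points.

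**Non-concurrent share.**
- Early controls: 145/4 = 36.25.
- N=225: late controls (225 - 145)/5 = 16; share 36.25/52.25 = 0.694.
- N=300: late controls (300 - 145)/5 = 31; share 36.25/67.25 = 0.539.
- Later switches raise it. At 160: 40/53 = 0.755 (N=225) and 40/68 = 0.588 (N=300). At 180: 45/54 = 0.833 and 45/69 = 0.652.

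**Bias.** Let drift be the late minus the early nitrofurantoin rate. The pooled control rate falls short of the late rate by share x drift, so the Group 4 difference is off by share x drift. For 5 points: 0.694 x 5 = 3.5 (N=225), 0.539 x 5 = 2.7 (N=300). For 10 points: 6.9 and 5.4. A negative drift reverses the sign.

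**Effect on the decision quantities.** Both binomials were enumerated with whole numbers (16 v 36+16; 31 v 36+31), late control rate 0.82, early rate 0.82 minus drift. The exact interval is taken as unconditional and score-ordered, since 7.2 does not name the method. The 0.80 event borrows the SAP 3.1 target.

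| Group 4 truly 10 points worse | drift -10 | -5 | 0 | +5 | +10 |
|---|---|---|---|---|---|
| Exact CI declares non-inferiority, N=225 | 0.2% | 0.6% | 1.3% | 2.7% | 5.0% |
| Same, N=300 | 0.4% | 0.9% | 1.8% | 3.5% | 6.3% |
| Posterior at least 0.80, N=225 | 10% | 15% | 22% | 30% | 39% |
| Same, N=300 | 8% | 13% | 20% | 29% | 39% |

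If Group 4 is truly equal, downward drift costs it. The chance of reaching 0.80 at drift 0/-5/-10 is 54/43/33% (N=225) and 63/52/40% (N=300).

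**Precision of the alternatives.** Standard errors at 0.82, with 0.82 x 0.18 = 0.1476:
- Pooled, N=225: sqrt(0.1476 x (1/16 + 1/52)) = 11.0 points; N=300: 8.3.
- Concurrent only, N=225: sqrt(0.1476 x 2/16) = 13.6; N=300: 9.8.
- Arm plus period over all arms: 11.7 and 8.7.

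Root-mean-square error (variance plus squared bias, then the square root) of the pooled estimate at drift 0/5/10 is 11.0/11.7/13.3 at N=225 and 8.3/8.9/10.1 at N=300. The concurrent estimate stays at 13.6 and 9.8.

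**Assumption behind the period term.** It needs drift common to all arms. The weight left on the early controls is 0.519 (N=225) or 0.403 (N=300). If nitrofurantoin drifts 5 points more than Groups 1-3, that result is biased by 0.519 x 5 = 2.6 or 0.403 x 5 = 2.0 points.

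**The case against.** The strongest case is that nothing shows any drift, and it largely stands. SAP 8.2 expects "38 tablets during the treatment phase for subjects enrolled at the time preceding protocol amendment 2, and 56 tablets with amendment 2", but 56 - 38 = 18 fits six even doses of three tablets, and Protocol Table 2 makes those tablets placebo in every arm except Group 4. Exclusions 3 and 4 ended at Amendment 1, not at the switch. Both are weak evidence, and a reader who infers documented drift from them goes beyond the documents.

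Four other strong readings are tempting and unsupported.
- That the concurrent-only comparison must govern. It removes the bias, but at N=225 the pooled estimate has the smaller root-mean-square error even at a 10-point drift; at N=300 it loses only near 10 points (10.1 v 9.8).
- That 0.80 decides the final analysis. SAP 3.1 says "The target probability is 0.80" for sample size, and Protocol 12.7 uses 80% to adjust recruitment. SAP 7.2 gives no posterior cut-off, so those figures only illustrate.
- That the plan has no period analysis. SAP 7.2 points to 7.5.2 for sensitivity analyses and Protocol 12.5.1 promises further Bayesian modelling. Section 7.5 and parts of 7.3 are redacted.
- That Groups 1-3 share the problem. They do only if an interim changed allocation ratios.

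Inference is also nominal (SAP 5.1.4). That limits the weight of any declaration, but it does not make a biased estimate unbiased.

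**Conclusion.** The concern holds for the visible primary analysis. Under equal allocation and a switch at 145, 54% to 69% of Group 4's controls are non-concurrent, and the share rises if more subjects came first. A 5-point change in nitrofurantoin success would move the Group 4 difference by 2.7 to 3.5 points, in a direction that cannot be known in advance. Under the exact-interval rule a 5-point rise takes the one-sided error to 2.7% (N=225) or 3.5% (N=300), which is modest.

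Whether drift occurred is unknown; 5 and 10 points are assumed values. The case for change is that 7.2 attaches a per-dose declaration to a partly non-randomised comparison and shows the reader nothing against which to check it. The documents do not settle which adjusted analysis is best.

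**What to change.** In SAP 7.2, for Group 4, report beside the pooled result, each for both the confidence interval and the posterior:
1. the comparison with nitrofurantoin subjects randomised under Amendment 2;
2. an analysis over all arms with a randomisation-period (protocol version) term, stating that it assumes drift common to all arms.

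State that Group 4 non-inferiority will not be declared on the unadjusted pooled comparison alone, and that disagreement between the results will be reported as a limitation. If redacted 7.5 already does this, a citation in 7.2 is enough. Which of the two governs, and the interval method, are for the sponsor to choose. Extend this to Groups 1-3 only if allocation ratios changed.

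The cost is SAP wording, a little more analysis and a variable already used in SAP 8.2. The adjusted results are less precise: at N=225, a standard error of 13.6 points (concurrent) or 11.7 (period term) against 11.0 pooled; at N=300, 9.8 or 8.7 against 8.3.
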